## 2 List of abbreviations

ACCF	American College of Cardiology Federation
AE	Adverse Events
AHA	American Heart Association
AIDS	Acquired immunodeficiency syndrome
Alb	Albumin
ALP	Alkaline phosphatase
ALT	Alanine aminotransferase
AMI	Acute Myocardial Infarction
ART	Antiretroviral Therapy
ARV	Antiretroviral
BMI	Body Mass Index
Ca	Calcium
cART	Combination Antiretroviral Therapy
CD4+ cells	CD4+ T-cell count
CHD	Coronary Heart Disease
cIMT	Carotid artery Intima Media Thickness
Cl	Chloride
CMV	Cytomegalovirus
CPK	Creatinine phosphokinase
cPWV	Carotid-femoral pulse wave velocity
Cr	Creatinine
CrCl	Creatinine Clearance
CRF	Case Report Form
CVA	Cerebrovascular accident
CVD	Cardiovascular disease
CVE	Cardiovascular events
D.A.D –RS	D.A.D risk score
D.A.D.	Data collection on Adverse events of anti-HIV Drugs
DBP	Diastolic Blood Pressure
DSMB	Data Safety and Monitoring Board
ECG	Electrocardiograph
eGFR	estimated glomerular filtration rate
ESC	European Society of Cardiology
FBE	Full Blood Examination
FRS	Framingham Risk Score
GGT	Gamma- glutamyl transpeptidase
HaCH	HIV and Cardiovascular Health
Hb	Haemoglobin
HCO 3	Bicarbonate
HDL-C	High-density lipoprotein cholesterol
HIV	Human Immunodeficiency Virus
HMG Co-A	3-hydroxy-3-methylglutaryl coenzyme A
HUG	Geneva University Hospitals
hsCRP	High sensitivity C-reactive protein
K+	Potassium
LDL-C	Low-density lipoprotein cholesterol
LFT	Liver Function Tests

LPS	Lipopolysaccharide
Lymp	Lymphocyte Count
MAC	Mycobacterium avian complex
MDRD	Modification of Diet in Renal Disease
Na	Sodium
Neut	Neutrophil Count
PBMC	Peripheral blood mononuclear cells
PBS	Pharmaceutical Benefits Scheme
PCP	Pneumocystis jirovecii pneumonia
Plt	Platelets
PML	Progressive multifocal leucoencephalopathy
PO 4	Phosphate
PVD	Peripheral vascular disease
RNA	Ribonucleic acid
SAE	Serious Adverse Events
SBP	Systolic Blood Pressure
SHCS	Swiss HIV Cohort Study
SLE	Systemic Lupus Erythematosus
Statin	HMG Co-A reductase inhibitor
TC	Total Cholesterol
TG	Triglycerides
TIA	Transient ischaemic attack
TP	Total Protein
UEC	Urea, Electrolytes and Creatinine
ULN	Upper limit of normal
Ur	Urea
VAS	Visual Analogue Scale
VIDRL	Victorian Infectious Diseases Reference Laboratory
WCC	Total White Cell Count
WHF	World Health Federation
β-HCG	Beta-human chorionic gonadotropin

### 3 Definition of Terms

Study medication	the medication under investigation (rosuvastatin) or the corresponding placebo product administered for blinding
------------------	--

## 4 Protocol Synopsis

**Protocol title:** Does rosuvastatin delay progression of atherosclerosis in people with HIV infection at moderate cardiovascular risk? A randomized, placebo-controlled trial

**Primary Objective:** The primary objective is to determine the effect of rosuvastatin on atherosclerosis progression in individuals with HIV infection who are at moderate cardiovascular risk.

**Study Design:** This study will be a randomized, double blinded, placebo controlled, multicentre trial comparing the effect of rosuvastatin 20mg daily versus placebo over 96 weeks in people with HIV infection who are at moderate cardiovascular risk (as estimated by a Framingham Risk Score (FRS) between 10 – 15%). Participants will be randomised 1:1 to active rosuvastatin 20mg once daily or matching placebo. Participants on a protease inhibitor will receive dose reduced rosuvastatin (10 mg).

**Planned sample size:** 102 HIV positive participants (72 participants in Melbourne and 30 in Switzerland)

### Inclusion Criteria

1. Provision of written, informed consent
2. Age >30 years
3. Moderate coronary heart Disease (CHD) risk, defined as FRS of 10-15%
4. HIV positive
5. Stable ARV regimen > 3 months (i.e. no recent drug change [changes in dosages are accepted])
6. Plasma HIV viral load <200copies/ml for  $\geq$  6 months

### Exclusion criteria

1. Recommended use of lipid lowering drug therapy according to Australian Guidelines (National heart foundation 2012)
2. Family History of myocardial infarction or stroke
3. Type 2 Diabetes
4. Familial hypercholesterolemia
5. Aboriginal or Torres Strait Islander people with LDL-C >2.5 mmol/L
6. Blood pressure  $\geq$  180/110
7. Documented history of:
  - a. Ischemic stroke or transient ischemic attack (TIA)
  - b. Peripheral arterial disease
  - c. Congestive heart failure
  - d. Coronary artery disease or ECG findings consistent with prior MI
8. Carotid artery stenosis or >50% occlusion of the carotid artery
9. Total Cholesterol > 7.5 mmol/L
10. Triglyceride level >4.0 mmol/L
11. HDL-c <1 and Total cholesterol > 6.5 mmol/L
12. Current or prior (last 6 months) statin, ezetimibe, fibrate or niacin therapy

13. Contraindication to statin use
  - a. Pregnancy or lactation
  - b. Hypersensitivity to statins
  - c. Known myopathy or baseline CK > 3x ULN
  - d. Contraindicated concurrent medication
  - e. Current cyclosporine, fusidic acid or oral corticosteroid use
14. Concomitant antiplatelet drug
15. Unable to complete study procedures
16. Any active, clinically significant disease
17. Concomitant renal or hepatic disease, defined as the presence of the following:
  - a. Creatinine Clearance <50ml/min
  - b. Transaminase (ALT, AST) above 3 times upper normal limit
  - c. Acute hepatic failure
  - d. Compensated cirrhosis Child Class B or C

**Study procedures**

Carotid intima media thickness (cIMT), carotid-femoral pulse wave velocity (cPWV) and biomarkers of immune activation and inflammation will be measured at baseline and compared to values obtained after 48 and 96 weeks of treatment with the study medication. Other procedures will include assessments of safety, fasting lipid and glucose analysis and storage of plasma and peripheral blood mononuclear cells (PBMCs) for future research.

## 5 Flow Chart

Assessment	Screen	Baseline	Post randomization				
Week	-4	0	12	24	48	72	96
Written Informed consent	X						
Inclusion / exclusion criteria	X						
Demographic questionnaire a	X						
Physical examination b	X	X			X		X
Compliance assessment c					X		X
Weight & Height measurement d	X				X		X
Adverse event assessment e		X	X	X	X	X	X
Risk Score Calculation f	X						
Laboratory Assessments							
T Cells	X		X	X	X	X	X
HIV RNA viral load	X		X	X	X	X	X
FBE g	X	X	X	X	X	X	X
Biochemistry h	X	X	X	X	X	X	X
Fasting Lipids/glucose i	X	X		X	X		X
hsCRP		X	X				X
Research Blood samples j		X	X		X		X
Structural assessments							
Carotid IMT k	X				X		X
Pulse Wave Velocity l	X				X		X

a Demographic data, medical history and medication questionnaire (will be performed with a trained interpreter if required)

b Includes blood pressure measurement, cardiovascular examination; electrocardiogram (ECG) at screening visit only

c See appendix 17.2: Compliance self-assessment questionnaire and visual analogue scale

d Height will only be measured at screening visit. Body Mass Index (BMI) will be calculated at screening and 12 and 24 month post randomisation

e Unscheduled visits may be performed for safety/tolerability concerns

f Framingham (FRS) and Data Collection on Adverse Events of Anti-HIV Drugs (D.A.D) risk scores calculated

g Full Blood Examination: Haemoglobin, White cell count, Lymphocyte count, Neutrophil count, Platelet count

h Including sodium, potassium, bicarbonate, chloride, calcium, phosphate, urea, creatinine; Liver function tests (LFTs): alanine aminotransferase (ALT), alkaline phosphatase (ALP), total protein, albumin; creatinine phosphokinase (CPK), pregnancy screen in women with child bearing potential

i Participants will fast overnight and have bloods taken in the morning for total cholesterol (TC), low-density lipoprotein cholesterol (LDL), high-density lipoprotein cholesterol (HDL), triglycerides (TG) and glucose

j Blood for markers of innate immunity and inflammation; see Section 11.2 for full description of testing to be performed and stored bloods for future projects

k Carotid intima media thickness (cIMT) will be performed on the left and right common carotid arteries, 12 consecutive measurements will be made 1-3cm proximal to the carotid bulb in areas identified as being without plaque.

l Carotid-femoral Pulse Wave Velocity (cPWV) will be determined by using simultaneous applanation tonometry of the carotid and femoral arteries. Only for Australian site.

## 6 Background

### 6.1 Relationship between HIV infection and CVD

#### **HIV positive patients have a two-fold increased risk of CVD**

cART has dramatically reduced HIV-related morbidity and mortality resulting in a rapidly growing population of older patients living with HIV. The major burden of illness, health care utilization and premature death in people with HIV is now due to diseases of ageing, particularly CVD, which occurs not only at higher rates (2 fold increased relative risk) but also at a younger age than in the general population. In a case-control study performed at the Alfred Hospital (AH) in 2010, the incidence of cardiovascular events (CVE) in HIV positive people was 8.5 cases per 1000 person years, twice the rate reported rates in HIV negative males of similar age (3.9 per 1000 person years). HIV may promote atherogenesis by a reduction in high-density lipoprotein cholesterol (HDL-C) and reverse cholesterol transport, immune activation and inflammation, increases in thrombosis and fibrinolysis and endothelial dysfunction.

Cardiovascular risk is likely to be underestimated in people with HIV. The contributing effect of HIV-associated immune activation and cART on CVD risk in HIV positive people is not considered in traditional CVD risk scores (such as the FRS). In a cohort study conducted by our group at the AH, the FRS correlated only moderately with carotid intima media thickness (cIMT), a well validated surrogate marker of CVE. 11% of HIV positive patients with low (<10%) FRS had a cIMT >0.7 mm (*HIV and cardiovascular health (HaCH) study pilot data*). Whilst others have also shown the true CVD risk is likely to be underestimated by FRS in people with HIV, correlation between FRS and risk of CVD in HIV patients remains uncertain.

#### **CVD is associated with immune activation and inflammation in people with HIV.**

The increased risk of CVD in HIV positive people is thought to be due to a combination of the effects of HIV infection, toxicity from ART and conventional CVD risk factors. The Data collection on Adverse Effects of Anti-HIV Drugs (D:A:D) study, (including data from the AH HIV cohort) provided the first evidence of increased incidence of myocardial infarction with longer duration of cART (26% increased rate of AMI per year of ART use), in addition to different relative risks according to class of ART used and specific ART drugs. HIV infection is associated with chronic immune activation and inflammation that persists despite virologic suppression. The increased risk of CVD decreases with successful ART, but does not return to that of the general population. It is also known that increased levels of T cell activation in HIV positive participants predicts subclinical carotid artery disease.

The pathogenesis of atherosclerosis is complex but inflammation is a key driving force. Inflammation drives oxidation of plasma low-density lipoprotein (LDL-C) and activates endothelial cells allowing monocytes to attach to them via their CD11b receptor and then migrate into the forming atherosclerotic plaque within the vessel wall. Bacterial endotoxin or lipopolysaccharide (LPS) is a potent inducer of inflammation; chronic endotoxemia and high plasma soluble CD14 (sCD14, released from monocytes and macrophages) are found in most HIV positive people. This is secondary to HIV-induced CD4+ T-cell depletion in the gut and loss of mucosal integrity allowing translocation of microbial products (e.g. LPS) across the gut. LPS binds to monocytes via CD14, signalling cellular activation and pro-inflammatory

cytokine (e.g. IL-6) production that is critical for the initiation of CVD. Production of CRP in the liver is primarily driven by IL-6, which activates further IL-6 production by monocytes.

## 6.2 Surrogate markers of cardiovascular outcomes

Given the large number of patients that have been required to perform clinical outcome studies in CVD it is neither feasible nor practical to design such a study in the HIV population. . Thus surrogate markers of CVD endpoints are necessary to allow to effects of therapeutic interventions on CVD risk to be assessed in this population. In this study we will be utilising two well validated surrogate markers of CVD; cIMT and cPWV.

### **Carotid intima media thickness**

cIMT has been validated as an independent predictor of CVD outcomes in the general population after adjustment for other risk factors. cIMT has been used as an endpoint in clinical trials evaluating the effect of statins on CVD outcomes with a correlation between treatment induced reductions in cIMT and AMI. Several cross-sectional studies have shown HIV+ people have greater cIMT than age and sex matched controls, and significantly higher progression rates than historical reports in HIV negative populations.

### **Pulse Wave Velocity**

cPWV is a surrogate measure of arterial stiffness and is considered a marker of atherosclerosis. It has been shown to be an independent predictor of CVD events in prospective studies. Increased arterial stiffness has been reported in HIV infection compared with HIV negative controls. Rosuvastatin has been shown to improve aortic arterial stiffness with changes strongly correlated with reduction in LDL. cPWV will not be performed at Swiss sites.

## 6.3 Statin therapy

Statins are HMG-CoA reductase inhibitors that lower total cholesterol, improve endothelial function, and halt progression of atherosclerosis. Randomized trials of rosuvastatin in the general population have shown a reduction in major CVD events and in the inflammatory biomarker high sensitivity C-reactive protein (hsCRP) in healthy adults with normal LDL levels (the JUPITER trial). High levels of baseline hsCRP were an independent predictor of CVD in this cohort. The absolute CVD event reduction with rosuvastatin was greatest in those with highest baseline hsCRP levels and in those who achieve low hsCRP levels regardless of LDL level achieved. The cIMT effect size seen with statin therapy correlates with reduction in LDL and baseline cIMT. As previously shown HIV positive people have, on average, greater cIMT and faster cIMT progression rates, thus it is likely that the magnitude of effect seen with statin therapy may be greater.

Furthermore, statins are immune modulators, and inhibit inflammation in part by reducing chemokine and pro-inflammatory cytokine synthesis by monocytes, inhibiting monocyte adhesion to the blood vessel wall as well as improving the function of other cells involved in atherogenesis (smooth muscle cells, platelets, endothelial cells). Rosuvastatin is predicted to alter the plasma levels of inflammatory markers and monocyte phenotype by week 12. Atorvastatin decreased CRP, IL-6 and CCL2 levels in 4 -6 weeks in HIV negative participants. Rosuvastatin has been shown to induce a 16% reduction in hsCRP in stable ART-treated HIV positive participants over 45 days. High dose atorvastatin over 8 weeks in ART naive HIV positive participants resulted in significant decreases in immune activation (CD4+ HLA-DR+, CD8+ HLA-DR+ and CD8+ CD38+ T cells). These effects may provide

additional benefit in HIV positive participants given high baseline levels of immune activation and inflammation and the association between these markers and CVD outcomes.

#### 6.4 Selection of doses

The Jupiter study, using a rosuvastatin dose of 20 mg daily, demonstrated reductions in LDL cholesterol by 50% and hsCRP by 37%; resulting in a 50% reduction in vascular events. The METEOR study reported a significant reduction in cIMT progression after 12 months of rosuvastatin therapy with the divergence continuing to increase with further follow-up out to 24 months. Most rosuvastatin (90%) is excreted unchanged, while 10% undergoes limited metabolism by cytochrome P450 2C9. Pharmacokinetic studies of drug-drug interactions in healthy volunteers have shown that protease inhibitors (PI) in current use caused a 2.4-4.7 fold increase in Cmax and 1.5-3 fold increase in AUC for rosuvastatin. For the participants receiving a non-PI based cART regimen, a dose of 20 mg rosuvastatin (1 x20 mg tablet) will be used. Participants on any PI-based cART regimen will receive 1 X 10 mg rosuvastatin (effective exposure 20 mg daily).

#### 6.5 Rationale for performing study

The key questions regarding CVD in HIV positive people is the extent to which the pathogenesis of CVD differs between HIV positive people and the general population, and whether treatment thresholds established in the general population for the initiation of conventional CVD interventions (such as statin therapy) apply to HIV positive people. Given the role of inflammation in atherosclerosis, strong evidence of higher cIMT and greater progression rates of cIMT in HIV infection it is plausible that HIV positive people may experience a clinical benefit from the earlier initiation of statin therapy.

This study will prospectively collect validated surrogate CVD endpoint data and extensive biomarker investigations in HIV positive participants, enabling controlled comparisons of these endpoints between the two treatment arms. It is likely that HIV positive patients at moderate FRS (who would not normally qualify for statin therapy on current guidelines) will experience quantifiable benefits from administration of rosuvastatin due either to higher baseline levels of atherosclerosis not reflected in FRS or due to differential immunological effects in the unique milieu of immune activation seen in HIV positive people.

#### 6.6 Sample size

The METEOR study of rosuvastatin in HIV negative participants with low to intermediate CVD risk found a mean Common Carotid Artery cIMT progression rate of 0.0088 mm/2 years in the placebo arm and 0.0004mm/2 years in the rosuvastatin arm^22, giving an effect size of 0.0084 mm/2 years (95% relative reduction) with a standard deviation (SD) of 0.033 mm/year. A pilot study in HIV positive patients at the AH (n=10) found that in participants treated with non-nucleoside reverse transcriptase inhibitors (the most common cART regimen), the mean cIMT progression rate was 0.04 mm/year with a SD of 0.0782 mm (personal communication [name], Baker IDI), similar to estimated values proposed for cIMT progression in HIV positive participants at low to intermediate CVD risk (mean 0.045 mm/year, SD 0.08 mm; 62).

Conservatively assuming a cIMT progression rate of 0.080 mm with a SD of 0.09 mm over 2 years and near stabilisation of cIMT (95% relative reduction) with rosuvastatin, we can assume an effect size of 0.076 mm with a SD of 0.09 mm. Sample size was calculated using an independent groups t-test with an alpha threshold of 1% and a power of 90%. Based on these hypotheses, with 44 participants in each group this study will be able to detect an effect

size of 0.076 mm with a SD of 0.09 mm over 2 years between the 2 groups. With an estimated 15% total drop-out rate over 96 weeks, we estimate that a total study population of 102 will be required.

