## 8.2 Duration

Ninety-six (96) weeks per patient

Expected duration for entire project – 5 years

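### Section 6.6 powers the trial on a 2-year effect although the primary endpoint is at week 96; at the plan's own rate, power is about 84 to 86%, not 90%

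*Combined protocol and SAP*

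**What the plan says.** Section 6.6 (Sample size) cites two HIV sources. In the first, a pilot with n=10, "the mean cIMT progression rate was 0.04 mm/year with a SD of 0.0782 mm". The second gives a mean of 0.045 mm/year with an SD of 0.08 mm. The pilot SD is given in mm, and neither its time base nor the length of pilot follow-up is stated.

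The planning values are then set: "Conservatively assuming a cIMT progression rate of 0.080 mm with a SD of 0.09 mm over 2 years". With "near stabilisation of cIMT (95% relative reduction) with rosuvastatin", the section concludes that "we can assume an effect size of 0.076 mm with a SD of 0.09 mm". The test is a t-test for independent groups with "an alpha threshold of 1% and a power of 90" per cent, which gives 44 per group, and 102 in total after allowing for 15% drop-out.

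Section 8.2 (Duration) sets follow-up at "Ninety-six (96) weeks per patient". Section 17 runs the primary analysis from baseline to week 96, with measurements at baseline, week 48 and week 96. The drop-out allowance in Section 6.6 is itself expressed over 96 weeks, so that section uses two time bases.

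**The concern.** There are two separate points.

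**Time base.** An effect that takes 104 weeks to accrue has been assigned to an endpoint measured at 96 weeks. Under linear progression only 96/104 of it is present at the final scan. This follows from the plan's own figures and needs no new assumption about variability.

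**SD.** The mean goes from 0.04 to 0.080 mm, a factor of exactly 2. The SD goes from 0.0782 to 0.09 mm, a factor of 1.15. If the pilot SD is a one-year figure, the standardised effect rises from 0.95 × 0.04 / 0.0782 = 0.49 to 0.076 / 0.09 = 0.84. The section does not explain why the SD should grow so little, yet calls the choice conservative.

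The power figure will be used. A null result would be read as coming from a trial with 90% power. The stopping rules in Section 15 also let the DSMB consider futility when accrual or non-compliance leaves too little power for the specified benefit, and that benefit and power are defined only in Section 6.6.

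**Working it through.** All power values use the noncentral t distribution with 44 per group (86 df). The plan does not state sidedness. A two-sided 1% test reproduces 44 per group and a one-sided test gives 38, so two-sided is used. The critical value is 2.634 and the noncentrality is λ = δ / (σ √(2/44)), where √(2/44) = 0.2132.

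**1. The plan's own figure.** δ = 0.95 × 0.080 = 0.076 mm and σ = 0.09 mm. λ = 0.076 / (0.09 × 0.2132) = 3.96, so power is 90.5%. The stated 44 and 90% are reproduced.

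**2. Effect at 96 weeks, SD unchanged.** With linear progression, δ = 0.076 × 96/104 = 0.0702 mm. λ = 0.0702 / (0.09 × 0.2132) = 3.66, so power is 84.4%. Restoring 90% at these values would take 51 per group.

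**3. SD also brought to 96 weeks.** Take the pilot SD as a one-year figure (an assumption) and let the variance of change be V(t) = e + b t², where e is noise that does not grow with time and b is the between-person slope variance.

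- Year 1: e + b = 0.0782² = 0.006115
- Year 2: e + 4b = 0.09² = 0.008100
- So b = 0.001985 / 3 = 0.000662 and e = 0.005454
- Noise share of the one-year variance: 0.005454 / 0.006115 = 89%
- At t = 96/52 = 1.846: V = 0.005454 + 0.000662 × 3.408 = 0.00771, so the SD is 0.088 mm

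λ = 0.0702 / (0.0878 × 0.2132) = 3.75, so power is about 86%.

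**4. The second cited rate.** δ = 0.95 × 0.045 × 2 × 96/104 = 0.0789 mm. With SD 0.09 mm, power is about 93%.

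**5. Sensitivity to the SD, effect 0.070 mm throughout.**

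| SD (mm) | How it arises from the pilot SD | Power |
|---|---|---|
| 0.0782 | no growth with time | 94% |
| 0.09 | plan's value | 84% |
| 0.111 | × √2 | 63% |
| 0.156 | × 2, no measurement error | 30% |

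The last two rows use two-year multipliers. With 96-week multipliers, √(96/52) and 96/52, the SDs are 0.106 and 0.144 mm and power is 68% and 37%. The range is wide either way. If all ten pilot participants contributed and changes were normal, the 95% confidence interval for the pilot SD alone is about 0.054 to 0.143 mm.

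**The case against.** **The 90% is right for the inputs given.** This stands. A reader might infer a calculation error in Section 6.6, but the documents do not support that. The t-test, the alpha and 44 per group agree with one another; what is off is the time base of the effect.

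**Week 96 is treated as 24 months elsewhere.** The flow-chart footnote on BMI, Section 7.2 and Section 17 all use month labels for it. The visit window of plus or minus six weeks also allows a final scan at week 102. This explains the wording but does not remove the discrepancy. The scan is scheduled at week 96, and even the latest permitted visit falls short of week 104.

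**The second source supports the plan.** This stands in part. At 0.045 mm/year the 96-week effect is 0.079 mm, above the planned 0.076 mm, so the two cited rates bracket the planning value. The choice of words also has some backing: 0.080 mm is below that source's doubled mean of 0.090 mm, and 0.09 mm exceeds both cited SDs. However, the plan chose the pilot rate, and its power statement should follow from that rate. The cited SDs also sit beside annual means, so exceeding them does not show that 0.09 mm is cautious for two years.

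**An SD of change need not grow with time.** This stands. Where measurement error dominates, a 15% rise is plausible, and the documents give no error variance for cIMT by which to judge the 89% share. The pilot SD may not be a one-year figure at all. A reader might infer that 90% power holds only under the kindest scaling of the pilot. It does not: an SD that stayed at 0.0782 mm would give 97% at the 0.076 mm effect and 94% at 0.070 mm.

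**Conclusion.** The time-base point holds. At the plan's assumed rate, linear progression, 44 per group and two-sided 1%, power for the week-96 endpoint is about 84% with SD 0.09 mm and about 86% with the SD also at 96 weeks. That is 4 to 6 percentage points below the 90.5% that the stated inputs give. At the second cited rate it would be about 93%.

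The SD point holds only as missing justification. If the pilot SD covers one year, 0.09 mm at two years implies that about 89% of the one-year variance is noise that does not grow. The plan neither says so nor gives data to test it. *Conservatively* is therefore only partly supported.

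A reader might go further and take the trial to have 30% power. That figure needs the SD to double, which means no measurement error at all. It is the extreme of a sensitivity range, and the documents do not point to it as the likely case.

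**What to change.** In Section 6.6:

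1. Express the effect at week 96: placebo progression 0.080 × 96/104 = 0.074 mm and effect 0.070 mm at the pilot rate. State that the test is two-sided, if that is what was used.
2. Restate power at 44 per group as about 84% (SD 0.09 mm) to 86% (SD 0.088 mm), and note about 93% at the second cited rate with SD 0.09 mm.
3. Add the sensitivity at 0.070 mm on both sides of the planning SD: 94%, 84%, 63% and 30% at 0.0782, 0.09, 0.111 and 0.156 mm, with the last labelled as the no-measurement-error extreme.
4. State the time base of the pilot SD and how 0.09 mm was derived from it. Justify *Conservatively* on that basis or delete it.

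The sample size stays at 102. The cost is a few sentences and a slightly less favourable stated power. A pooled blinded SD from the week-48 scans could be reported as information on one-year variability, but it would not settle the 96-week SD, because how the SD grows from week 48 to week 96 is the open question.
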